1.2.1.5 Non-Clinical Studies of mTOR Pathway Inhibition in HCC

In vitro, mTOR activation appears exert an oncogenic effect on hepatocellular cell lines. In the non-hepatoma hepatocellular cell line HepaRG, a constitutively active mTOR mutation confers a premalignant phenotype, though mutations in mTOR, PTEN, and PIK3CA are rare in studies of clinical specimens. (Parent, Kolippakkam et al. 2007; Villanueva, Chiang et al. 2008) A significant proportion of resected HCC tumor specimens feature activation of the mTOR pathway, as measured by phosphorylation of one or multiple members of the mTOR cascade including mTOR itself, AKT, IGF-1R, 4EBP-1, p-RPS6, and p70S6K, or by increased levels of total p70S6K expression. (Sahin, Kannangai et al. 2004; Sieghart, Fuereder et al. 2007; Schmitz, Wohlschlaeger et al. 2008; Villanueva, Chiang et al. 2008; Baba, Wohlschlaeger et al. 2009) In a study of 166 liver explants with HCC from orthotopic liver transplant recipients, phosphorylated mTOR (p-mTOR) was identified by immunohistochemistry in 41% of tumors; p-mTOR was not identified in adjacent non-tumor cirrhotic tissue. (Sieghart, Fuereder et al. 2007) Phosphorylated p70S6K was present in 49% of HCC tumors in this study, and phosphorylated 4EBP-1 was present in 39%. There was no apparent correlation, however, between mTOR

activation and disease-free or overall survival. In another study of 101 resected hepatoma specimens, phosphorylated AKT (p-AKT) measured by immunohistochemistry was present with moderate levels in 50.5% and strong levels in 31.4%, by comparison with no staining in normal hepatocellular tissue.(Schmitz, Wohlschlaeger et al. 2008) Tumors with moderate and strong p-AKT expression were associated with a trend toward reduced tumor-specific overall survival (P = 0.059) in this study. Two other large studies of HCC resection specimens detected elevated levels of phosphorylated p70S6K in 24.5% and p-RPS6 in 47.7% of tumors, respectively, using immunohistochemistry; the presence of phosphorylated p70S6K or p-RPS6 was associated with poor clinical outcomes in both studies.(Villanueva, Chiang et al. 2008; Baba, Wohlschlaeger et al. 2009) Phosphorylated AKT, mTOR, and p70S6K have also been detected in HCC-associated sinusoidal endothelial cells by comparison to non-malignant liver tissues.(Li, Tan et al. 2008)

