1.4.3 Markers of mTOR Pathway Activation

Predictive biomarkers are essential to understand the efficacy of mTOR inhibition in HCC. Activation of the mTOR pathway (e.g. underexpression or loss of PTEN and/or LKB1, and/or overexpression of pAKT and/or pS6RP) is detectable by tumor immunohistochemistry (IHC) in approximately 50% of human HCCs and appears to be related to *in vitro* sensitivity to TORC1 inhibition in HCC cell lines.¹⁻³ Across tumor types, there are no clinically-validated markers of response to mTOR inhibitors.⁴ In a phase I/II study of everolimus in 28 patients with HCC, 3 of 11 patients with available baseline tumor specimens demonstrated activation of the mTOR pathway by IHC for pAkt (S473), pmTOR, and/or pS6RP (S235/236); the only patient with a PR in the study had moderate or high levels of each marker.⁵ A prolonged partial response to everolimus in an HCC patient with high tumor pS6RP expression has been described.⁶ LKB1 is a tumor suppressor which when deficient or deleted is associated with mTOR pathway activation, a metastatic phenotype and poor outcomes.⁷ Preclinical models of LKB1-deficient tumors suggest sensitivity to mTOR inhibition.⁷ A correlative objective will be to examine whether tumor mTOR pathway activation as measured by selected IHC markers and by tumor next-generation DNA sequencing of a targeted panel including mTOR pathway genes is related to clinical outcomes of TORC1 inhibition.

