7.3.2 Markers of mTOR Pathway Activation

Archival tumor blocks will be accessioned then sectioned into 5 µm slides (3-5 plus H&E) and submitted to the UCSF Immunohistochemistry Core to perform IHC for selected mTOR pathway activation markers such as pAKT (S473), pS6RP (S235/236), PTEN (rabbit polyclonal antibody PN37), and LKB1 (D60C5). Optimization for each antibody will be performed using breast tumor samples as positive controls. The Director of the Core, [REDACTED], will read and provide reports for each case including intensity (0-3+), percentage positivity, distribution (very focal, focal, diffuse), and intracellular localization (membranous, cytoplasmic, nuclear) for each stain.⁷⁻¹⁰

In addition, FFPE sections from consenting patients will be submitted to the UCSF Clinical Cancer Genomics Lab (CCGL) for sequencing using hybridization-based target enrichment to analyze ~539 cancer-related genes for mutations (including mTOR pathway genes such as mTOR, AKT, TSC1/2, PTEN, PIK3CA) and copy number changes; selected genes will be analyzed for structural rearrangements (<http://cancer.ucsf.edu/CCGL>). Paired whole blood samples also will be sequenced for germline comparison.

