9.4.4 Exploratory Analyses/Assessments

- CTC levels: Baseline level of CTC (detectable or undetectable) will be compared to proportion with TTP at 6 months to determine if there is an association using Fisher's Exact tests. Change in CTC levels (increase or decrease) after 1 and 2 cycles will be compared to proportion with TTP at 6 months to determine if there is an association using Fisher's Exact tests. Markers of mTOR pathway activation: Descriptive statistics will summarize the IHC parameters of staining intensity, percentage positivity, distribution, and intracellular localization for each protein. Due to possible limited specimen quantity, IHC outcomes will be dichotomized. Activation will be measured by % positive cells and intensity using published IHC cutpoints for high/low: cytoplasmic pAkt > 40% or 2-3+, cytoplasmic PTEN intensity < 10% or 0-1+, cytoplasmic pS6RP > 70% or 2-3+, or LKB1 0-1.⁷⁻¹² Univariate analysis using Cox's model will be performed to test whether the dichotomized expression of each protein using the published cutpoints is a significant predictor of TTP. Results for each test will include the hazard ratio (HR) with 95% confidence intervals. The association between each protein and the two binary coding schemes for AFP decline ($\geq 50\%$ or $\geq 20\%$) on C2D1 will be tested using Fisher's exact test. Results for each test will be summarized with proportions with pathway activation and 95% confidence intervals for each AFP subset. Each patient will also be categorized as having overall mTOR pathway activation (defined as any combination of high pAKT, high pS6RP, low PTEN, and/or low LKB1) or not. This binary variable will also be examined for its relationship with TTP, OS, AFP response, and other clinical endpoints using the same methods described above. For each test of association with AFP change, based upon Fisher's exact test large differences can be detected (e.g. 10% among 7 patients with marker-low, 80% among 8 patients with marker-low) (power=81%, $\alpha_2=10\%$). The sample size is too small to test for a difference in TTP, OS, or other clinical endpoints according to pathway activation status. The expected sample size will be ≥ 25 cases (expect 40 to 45 cases) with IHC-quality archival tumor, with the expectation that $\sim 75\%$ of cases will be evaluable for TTP ($n \geq 18$) and 60% evaluable for AFP response on C2D1 ($n \geq 15$).

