Genotype findings will be dichotomized as presence or absence of any mTOR pathway aberration or combination thereof (e.g. mutations in AKT, mTOR, PTEN, PIK3CA, and/or TSC1/2). This binary variable will be examined for its relationship with time to progression, overall survival, AFP response, and other clinical endpoints by univariate analysis using Cox's model. Concordance between primary and metastatic specimens on mutational profile will be described individually due to small sample size. Other tumor genotype findings and relationship to clinicopathologic covariates will be reported descriptively.

To optimize sample size and ensure adequate number of evaluable cases, these analyses of mTOR pathway IHC and genotype markers will also be performed on cases and samples CC#09455 when available, to ensure at least 25 evaluable cases with adequate archival tumor for testing. Although pooling of data and specimens across studies introduces potential confounding, it is appropriate for these exploratory analyses as the eligibility criteria and protocol therapy were overlapping for CC#09455 and the current study.

- Hepatitis B viral load: In all patients with active HBV infection, changes in HBV DNA quantitative by PCR (conversion from undetectable at baseline to detectable on study or an increase by $\geq 50\%$ from baseline versus unchanged from baseline) will be characterized using descriptive statistics (mean, median, standard deviation, and 95% confidence interval) to calculate the proportion of patients with an increase in viral load while on protocol therapy.
- Future biomarker research on banked specimens will be reported outside of the main study report

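### The 81% power given for each marker-by-AFP test is right for a near-even split but not for every marker at N=15, and Cox's model is assigned to AFP response

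*Combined protocol and SAP*

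**What the plan says.** The marker part of section 9.4.4 dichotomises each of four IHC stains (pAKT, pS6RP, PTEN, LKB1) at published cut-points. For pAKT, high means more than 40% positive cells or intensity 2-3+. A fifth variable, overall pathway activation, is positive if any of the four is abnormal. Each is tested against AFP decline on Cycle 2 Day 1 with Fisher's exact test.

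The power statement is general: "For each test of association with AFP change, based upon Fisher's exact test large differences can be detected". Its example is "10% among 7 patients with marker-low, 80% among 8 patients with marker-low", with power 81% at two-sided 10%. The number of cases is given as at least 25 with 40 to 45 expected, of which "60% evaluable for AFP response on C2D1".

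The reason given for the binary coding is "Due to possible limited specimen quantity, IHC outcomes will be dichotomized". Section 7.3.2 says the core reports each stain "including intensity (0-3+), percentage positivity, distribution" and localisation.

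On prevalence, section 1.2.1.5 reports p-AKT "present with moderate levels in 50.5% and strong levels in 31.4" percent of 101 resected tumours and, from another resection series, elevated p-RPS6 in 47.7%. Section 1.4.3 says pathway activation is "detectable by tumor immunohistochemistry (IHC) in approximately 50% of human HCCs".

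The genotype paragraph at the end of section 9.4.4 relates the binary genotype variable to time to progression, overall survival, "AFP response, and other clinical endpoints by univariate analysis using" Cox's model.

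**The concern.** The power of a two-group exact test depends heavily on how evenly the groups divide. The plan gives one near-even division and applies the result to every marker without linking it to any marker's expected prevalence. Where a marker is common or rare, one group may hold two or three patients, and a non-significant Fisher test then says little. A reader relying on the 81% could take such a result as evidence against the marker.

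Two errors of wording add to this. Both groups are labelled marker-low, so the example does not describe a comparison. The genotype paragraph gives AFP response, a binary outcome, a method that needs event times.

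**Working it through.** **Inputs.** Rates 10% v 80%, groups 7 and 8, two-sided 10%, power 81% (section 9.4.4; the second group is taken to be marker-high). AFP-evaluable cases: 0.60 × 25 = 15 at the minimum; 0.60 × 40 = 24 and 0.60 × 45 = 27 at the expected numbers. pAKT high: 50.5% + 31.4% = 81.9% (section 1.2.1.5), assuming that moderate or strong staining equals 2-3+. pS6RP high: 47.7% (same section). Overall activation: about 50% (section 1.4.3).

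**Formula.** With a responders among n₁ marker-low and b among n₂ marker-high patients, power = Σ Bin(a; n₁, 0.10) × Bin(b; n₂, 0.80) over all tables that Fisher's test rejects. Two conventions are shown: equal-tail (either one-sided p ≤ 0.05) and the usual two-sided p ≤ 0.10.

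**Step 1: the plan's figure.** At 7 low and 8 high, power is 81.4% equal-tail and 83.6% with the usual p-value. The 81% reproduces under the equal-tail convention.

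**Step 2: other splits of 15.**

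| Low:high | Equal-tail | Usual two-sided |
|---|---|---|
| 8:7 | 83.5% | 84.8% |
| 7:8 | 81.4% | 83.6% |
| 6:9 | 82.7% | 82.7% |
| 5:10 | 80.1% | 82.2% |
| 10:5 | 77.9% | 87.7% |
| 3:12 | 59.6% | 74.3% |
| 2:13 | 18.9% | 60.5% |
| 1:14 | 0% | 4.0% |

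Power stays near 80% down to five patients in the smaller group, and falls away at three or fewer.

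**Step 3: by marker at N=15.**
- pS6RP: 15 × 0.477 = 7.2 high, 7.8 low. Averaged over the binomial distribution of the split, power is 80.0% equal-tail and 83.9% usual.
- pAKT: 15 × (1 − 0.819) = 2.7 low. The chance of two or fewer low patients is P(Bin(15, 0.181) ≤ 2) = 47%. Average power is 39.6% equal-tail and 57.4% usual.
- PTEN and LKB1: no prevalence of low expression is given, so nothing can be computed.

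**Step 4: pAKT at the expected numbers.** Average power is 71.7% (equal-tail) to 81.3% (usual) at N=24, and 79.3% to 86.1% at N=27.

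**Step 5: consistency of the prevalences.** Overall activation is positive whenever pAKT is high, so its prevalence cannot be below that of pAKT. If pAKT is 81.9%, at most 2.7 of 15 patients are non-activated and the composite test is as uneven as the pAKT test. If the composite is about 50%, pAKT can be at most about 50%. The two figures cannot both describe this trial's population under the plan's definitions.

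**Step 6: Cox and AFP response.** For the IHC markers, section 9.4.4 uses Fisher's test against AFP decline and Cox's model for TTP. The genotype paragraph lists AFP response with TTP and overall survival under Cox's model alone. AFP response has no event time in the plan, so the two paragraphs treat the same outcome differently and only the first is workable.

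**The case against.** The strongest reply is that a reader might infer more than the documents support. Four stronger readings are tempting.

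*That the cited prevalences rule out a 7:8 split.* They do not. The 47.7% for p-RPS6 gives almost exactly that split. Nor is 7:8 needed: divisions from 5:10 to 10:5 give about 78% to 88%.

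*That a 50% composite implies about 16% for each marker.* That follows only if the four markers are independent (1 − (1 − x)⁴ = 0.5 gives x = 0.159). Section 1.2.1.4 places PTEN, AKT and downstream S6 kinase signalling in one cascade, so independence is implausible. The figure also disagrees with 47.7% for p-RPS6.

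*That the trial will have only 15 evaluable patients.* Fifteen is the stated floor. The plan expects more and pools the phase I samples to get there.

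*That graded scores should replace the cut-points as the main analysis.* The cut-points are published and prespecified, the graded data will be summarised descriptively, and no gain in power from switching has been shown.

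It is also fair that the 81% is offered as an example, that the section is exploratory, that no sample size or go/no-go decision depends on it, and that the 81.9% comes from one resection series, a specimen type that section 1.4 says may differ from advanced disease.

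These points limit the concern but do not remove it. The example is explicitly applied to each test and is built on 15 patients, so testing it at 15 is fair. The label and the Cox wording are wrong on any reading.

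**Conclusion.** The concern holds in limited form. The 81% is correct for a near-even split of 15 and reasonable for pS6RP. It does not hold for every marker at that number. For pAKT, average power is 40% to 57% at N=15 and 72% to 86% at N=24 to 27, for the plan's own 10% v 80% effect.

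The pAKT result rests on one assumption that the documents do not settle: that moderate or strong staining in the cited series matches the 2-3+ cut-point. If only strong staining (31.4%) counted, 15 × 0.314 = 4.7 patients would be high, and power at 10 low and 5 high would be 78% to 88% (70% to 80% averaged over the split). For PTEN and LKB1 the claim is unsupported rather than shown to be wrong.

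The conflict between 81.9% for pAKT and about 50% for overall activation must be reconciled before power for either variable can be stated. The duplicated label and the use of Cox's model for AFP response are plain errors.

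The stated reason for dichotomising is weak, because binary coding saves no tissue once a stain has been read. That supports adding a graded analysis, not dropping the published cut-points.

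**What to change.** In section 9.4.4:

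1. Say that the 81% applies to a near-even split of 15, name the two-sided convention used, and correct the second group's label to marker-high.
2. Replace the claim for each test with a short table of power by marker over the plausible splits at N=15 and at N=24 to 27. Where no prevalence is available (low PTEN, low LKB1), say so and show the range.
3. Reconcile the prevalence figures in sections 1.2.1.5 and 1.4.3 with the definition of overall activation, and state which figure is used for planning.
4. In the genotype paragraph, test AFP response with Fisher's exact test and keep Cox's model for TTP and overall survival only.
5. Optionally, add a supportive analysis of the recorded graded scores alongside the published cut-points, for example a Wilcoxon rank-sum test of the score by AFP decline.

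The cost is wording and one small table. No assay, sample or visit changes, because section 7.3.2 already has the graded readings reported.

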9.1.3 Secondary Endpoints

1. Response rate (RR) will be measured by RECIST version 1.1.

2. Median PFS will be calculated in months from date of first dose of protocol therapy to date of study removal for documented radiographic and/or clinical disease progression or death from any cause. For patients removed from study for other reasons than progression or death, PFS will be censored at the date last known to be progression-free.
3. Median OS for all enrolled patients who receive at least one dose of protocol therapy will be calculated from date of first dose of protocol therapy until date of death, using chart review and/or follow up phone calls to determine date of death in patients after removal from study. The survival of patients still alive after 5 years of follow up post study discontinuation will be censored.
4. TTF will be measured from date of first dose of protocol therapy to date of removal from study for progression, death, or toxicity. For patients removed from study for other reasons (such as noncompliance or withdrawal of consent), TTF will be censored at the date of study discontinuation.
5. In patients with baseline AFP ≥ 20 ng/mL, AFP response will be measured by the percent change from baseline value to the value at the time of best AFP response. The proportion of $\geq 50\%$ decline from baseline will be measured. The change in AFP will also be examined for association with absolute TTP and best response.
6. Toxicity will be measured using Common Terminology Criteria for Adverse Events (CTCAE) version 4.0. The frequency of dose reduction, treatment delays, and discontinuation for lack of tolerability will be quantified.

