9.4.3 Analysis of Secondary Endpoints

Response rates will be summarized and presented with 95% exact binomial confidence intervals. The comparison of response rates will use Fisher's exact test.

Kaplan-Meier methods will be used to summarize time-to-event outcomes including the primary endpoint (median TTP) and secondary endpoints (PFS, TTF, OS). Proportions of patients with TTP, PFS, and TTF equal to or exceeding 6 months will be calculated with 95% confidence intervals. Tumor response by RECIST 1.1 measurements will be presented descriptively for the study cohort.

- **AFP Response:** Baseline levels (high or low) will be compared to absolute TTP to determine if there is an association using Fisher's Exact tests or by Wilcoxon Rank-Sum test. Changes in levels on therapy with temsirolimus and sorafenib will be measured as an increase by $\geq 50\%$ from baseline, stable value within 50% of baseline, or decrease by $\geq 50\%$ from baseline. The change in level will be used to evaluate the predictive value for TTP. Fisher's Exact tests will be used to test for significance. Kaplan-Meier methods and Log-rank tests will also be used to estimate TTP based on the AFP.

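### Section 9.4.4 assigns AFP response to Cox regression in the genotype analysis, although the plan gives AFP response no event time and tests AFP decline with Fisher's exact test for the IHC markers

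*Combined protocol and SAP*

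**What the plan says.** **Genotype (9.4.4).** The predictor is binary: "Genotype findings will be dichotomized as presence or absence of any mTOR pathway aberration or combination thereof". One sentence then names the outcomes and a single method for all of them: "relationship with time to progression, overall survival, AFP response, and other clinical endpoints by univariate analysis using Cox's model".

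**IHC markers (9.4.4, preceding paragraph).** Here the method follows the outcome.
- For TTP: "Univariate analysis using Cox's model will be performed to test whether the dichotomized expression of each protein" predicts it, reported as a hazard ratio with a 95% confidence interval.
- For AFP: "The association between each protein and the two binary coding schemes for AFP decline" (at least 50% or at least 20%, on C2D1) "will be tested using Fisher's exact test. Results for each test will be summarized with proportions with pathway activation".
- The combined IHC activation variable is examined for its "relationship with TTP, OS, AFP response, and other clinical endpoints using the same methods described above", which carries the same matching forward.

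**Definition of AFP response (2.4.2 and 9.1.3, item 5).** In patients with baseline AFP of at least 20 ng/mL, "AFP response will be measured by the percent change from baseline value to the value at the time of best AFP response", together with the proportion declining by at least 50%.

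**AFP change and response rate (9.4.3).** AFP change is put in three categories (up by at least 50%, within 50%, down by at least 50%): "The change in level will be used to evaluate the predictive value for TTP. Fisher's Exact tests will be used to test for significance". The same section assigns comparisons of response rates to Fisher's exact test.

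**The concern.** In the genotype sentence AFP response stands as an outcome beside TTP and OS, so it cannot be read as a covariate in a model for TTP. A Cox model for it needs a date on which the response happened and a rule for patients in whom it did not. The plan supplies neither. The same difficulty reaches any of the other clinical endpoints that is not an event time, such as RECIST response.

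What is at stake is a correctly specified analysis of the one marker association for which 9.4.4 offers a power statement. That section says the sample is too small to test for differences in TTP, OS or other clinical endpoints by pathway activation, and reserves its power figure for AFP change. Left as it is, the genotype analysis of AFP would rest on choices made after the data are seen.

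**Working it through.** **1. How the plan itself treats AFP change.** Section 9.4.4 states 81% power at two-sided 10% for 10% of 7 patients against 80% of 8. (Both groups are printed as marker-low.) The group sizes agree with its evaluable number: 0.60 × 25 = 15 = 7 + 8. Enumerating both binomials and applying Fisher's exact test to every table gives:
- 81.4% with the two-sided p-value taken as twice the smaller tail, which reproduces the 81%;
- 83.7% with the minimum-likelihood two-sided p-value.

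The figure is therefore the power of a comparison of two proportions. No event time enters it.

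**2. Definitions side by side.**

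| Place | Form of the AFP outcome | Event time or censoring rule |
|---|---|---|
| 2.4.2, 9.1.3 | percent change to best value; proportion with at least 50% decline | none |
| 9.4.3 | three change categories | none |
| 9.4.4, IHC | decline of at least 50% or 20% on C2D1 | none |
| 9.4.4, genotype | AFP response, not further defined, by Cox | none |

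An analyst has two ways to run the model.

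**3. First way: one common time.** Illustrative data at the stated minimum of 15 evaluable patients: 4 of 5 altered and 4 of 10 unaltered patients respond, all at one visit. The split is an assumption; the documents give no genotype split.

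- Breslow estimate: 4/8 = 5e^b/(5e^b + 10), so e^b = 2.0. This equals the risk ratio, 0.8/0.4.
- Model-based standard error of the log hazard ratio: information = 8 × 0.5 × 0.5 = 2, so SE = 1/√2 = 0.707.
- Binomial standard error of the log risk ratio: √(1/4 − 1/5 + 1/4 − 1/10) = √0.20 = 0.447.
- Ratio: 0.707/0.447 = 1.58. The 95% interval is 2 × exp(±1.96 × 0.707) = 0.50 to 8.00, against 2 × exp(±1.96 × 0.447) = 0.83 to 4.80.
- Robust (sandwich) variance on the same fit: the squared score residuals sum to 4(0.1²) + 1(0.4²) + 4(0.3²) + 6(0.2²) = 0.80, so SE = √0.80/2 = 0.447, the binomial value.
- Other tie methods on the same data: Efron gives a hazard ratio of 2.69, and the exact discrete method gives 5.30.

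The point estimate thus runs from 2.0 to 5.3 with the tie method, and under Breslow the standard error is 0.71 or 0.45 according to the variance estimator. The plan states neither choice.

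**4. Second way: a time to AFP decline.** AFP is drawn on Day 1 of each cycle (6.1.2 and Table 6.1), so such a time could be constructed. It would need a threshold, an event date and a censoring rule, including for patients removed for progression. None of these is in the plan.

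**The case against.** The strongest reply is that this is loose wording in an exploratory paragraph whose intent can be recovered. The IHC text matches method to endpoint, the power statement rests on Fisher's exact test, and 9.4.3 already sends response rates to Fisher's exact test. The last point stands: for RECIST response the fix only repeats an existing rule. For AFP response the intent is a fair guess, but the genotype sentence does not refer back to the earlier methods as the IHC activation sentence does. It names Cox alone.

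Three stronger readings are tempting, and the documents support none of them.

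- **That the Cox result would be meaningless for a binary outcome.** With a common time and Breslow ties the hazard ratio equals the risk ratio, the model-based interval errs on the conservative side, and a robust variance removes the error. The 58% excess in the standard error belongs to one assumed combination of tie method and variance.
- **That sparse genotype groups would leave no finite interval.** Section 1.2.1.5 calls mutations in mTOR, PTEN and PIK3CA rare, but the variable counts any pathway aberration, including AKT and TSC1/2. Section 9.4.4 expects 40 to 45 IHC-quality cases; 60% of those is 24 to 27 evaluable for AFP. No carrier number is given. The 50% AFP response in the phase I trial (8 of 16, Section 1.2.3.1) is best response, not C2D1. With no responders among carriers only the Wald interval fails. For example, with 0 of 3 altered and 6 to 8 of 12 unaltered patients responding, the profile-likelihood upper limit is 1.09 to 1.51. A risk or odds ratio from the 2×2 table has the same Wald problem.
- **That AFP response cannot have an event time.** It could be given one from the per-cycle measurements. The time is undefined, not unobtainable.

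It is also true that the genotype sentence does not repeat the C2D1 codings, so treating its AFP response as the IHC outcome rests on the shared name.

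**Conclusion.** The genotype sentence assigns a time-to-event model to an outcome that the plan defines without a time, and it departs from the method given one paragraph earlier for AFP decline. That holds from the text alone.

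The size is modest. With a common time, the illustrative example gives a model-based standard error of 0.71 where 0.45 is right, too conservative, and a hazard ratio between 2.0 and 5.3 depending on an unstated tie method. These figures assume 15 patients, a 5/10 split, and response counts that are not in the documents. The alternative route is an endpoint nobody has specified.

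The effect is confined to an exploratory analysis. The primary TTP result, the safety monitoring and the decision on a randomized trial do not depend on it.

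**What to change.** Replace the single-method sentence in the genotype paragraph of 9.4.4 with wording to this effect:

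- Univariate Cox regression is used for event-time endpoints: TTP, OS, PFS and TTF.
- Binary AFP decline is compared between genotype groups with Fisher's exact test, using the codings already stated for IHC (at least 50% or at least 20% on C2D1). Proportions are reported with exact confidence intervals.
- The proportion with at least 50% decline at best AFP response (9.1.3) may be tested in the same way. This keeps later declines in view, which a C2D1 coding alone would miss.
- RECIST response is compared with Fisher's exact test, as 9.4.3 already says.

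If a time to AFP decline is really wanted, it should be defined as an endpoint of its own, with its threshold, event date and censoring rule.

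The cost is one sentence of analysis text. No new data, visits or patients are needed.
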